September 1, 2014

Study Title: Measurement of Cerebral Blood Flow Using Transcranial Doppler Ultrasound in Children with Sickle Cell Disease NCT: NCT02090881 Protocol ID: 13HH0858

Patients with SCD age 2 to 16 years attending our tertiary paediatric haematology clinic for stroke surveillance were eligible. The study was conducted as part of a higher degree in vascular imaging and hence the study duration was limited to six months. Based on patient numbers within the service, we aimed to study 25 consecutive patients referred to the vascular sciences department for routine TCD scanning. Ethical approval was obtained from the local research ethics committee (ref 13/LO/1503) and IRAS ID 133045) and written informed consent was obtained from legal guardians. A pulsatile flow simulating phantom was used to eliminate patient variability. Study participants were scanned by a single operator with imaging TCCD. Initially a full TCD assessment was performed using the non-portable Philips IU-22 with a S5-1 phased array transducer (5.0-1.0MHz). The measurement was then repeated in every patient in only the MCA on each side of the head using the portable Zonare Z-One scanner with a P4-1C phased array transducer (4.0-1.8MHz). For both examinations, a standardised screening protocol was used recording velocities from the transtemporal windows, a 5mm sample volume size, with no angle correction. Gain was adjusted in order to clearly see the spectral Doppler velocity waveform without the presence of noise in the background. For the purpose of this study, the TAMM velocities were compared because stroke risk categorisation according to the STOP trial was based on TAMM velocity, not peak systolic or end diastolic velocities. Each study was categorised as normal, conditional, abnormal or inadequate according to criteria previously developed by the STOP protocol. The participants were not permitted to sleep during the scan to avoid increase in blood carbon dioxide levels in sleep, which can result in increase in TCD velocities. Methods Patients with SCD age 2 to 16 years attending our tertiary paediatric haematology clinic for stroke surveillance were eligible. The study was conducted as part of a higher degree in vascular imaging and hence the study duration was limited to six months. Based on patient numbers within the service, we aimed to study 25 consecutive patients referred to the vascular sciences department for routine TCD scanning. Ethical approval was obtained from the local research ethics committee (ref 13/LO/1503) and IRAS ID 133045) and written informed consent was obtained from legal guardians.

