
A pulsatile flow simulating phantom was used to eliminate patient variability. Study participants were scanned by a single operator with imaging TCCD. Initially a full TCD assessment was performed using the non-portable Philips IU-22 with a S5-1 phased array transducer (5.0-1.0MHz). The measurement was then repeated in every patient in only the MCA on each side of the head using the portable Zonare Z-One scanner with a P4-1C phased array transducer (4.0-1.8MHz). For both examinations, a standardised screening protocol was used recording velocities from the transtemporal windows, a 5mm sample volume size, with no angle correction. Gain was adjusted in order to clearly see the spectral Doppler velocity waveform without the presence of noise in the background. For the purpose of this study, the TAMM velocities were compared because stroke risk categorisation according to the STOP trial was based on TAMM velocity, not peak systolic or end diastolic velocities. Each study was categorised as normal, conditional, abnormal or inadequate according to criteria previously developed by the STOP protocol. The participants were not permitted to sleep during the scan to avoid increase in blood carbon dioxide levels in sleep, which can result in increase in TCD velocities.

Study Title: Measurement of Cerebral Blood Flow Using Transcranial Doppler Ultrasound in Children with Sickle Cell Disease NCT: NCT02090881 Protocol ID: 13HH0858 Statistical Analysis Spearman's Correlation Coefficients were calculated to assess the relationships between different parameters in

September 1, 2014

order to assess the strength of the association between the two measures. Intra-class Coefficient Correlation (ICC) and 95% confidence intervals were used to provide a measure of the strength of the association between the measurements from both pieces of equipment and therefore the validity of the measurement. It has been stated that $ICC > 0.75$ implies acceptable validity.

BlandAltman plots were used to estimate the agreement between TAMM velocity measurements by determining how much the velocity from one machine differs from another. Statistical analyses were performed using SPSS Statistics version 21 (IBM). The level of statistical significance was defined as $p < 0.05$.

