Conclusion The purpose of this pilot study was to evaluate the use of a portable ultrasound machine by comparison with an established laboratory-based ultrasound machine. This study demonstrated complete agreement in stroke risk categorisation between the two instruments. As a pilot study, it confirms the feasibility and clinical significance of this investigation. A larger sample size with a greater range in TAMM velocities is needed to further investigate the correlation between different ultrasound machines at extremes of measurement such as very high or very low velocities. Further evidence is needed in order to establish the implications these differences may have on screening

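### The between-machine TAMM differences are never set against the STOP cut-points, so the screening conclusion rests on an unqualified statement of category agreement

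*Combined protocol and SAP*

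**What the plan says.** All references are to the combined protocol and SAP, whose sections are unnumbered.

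- **Sample (Methods).** "Based on patient numbers within the service, we aimed to study 25 consecutive patients". The target comes from service numbers and a six-month limit, not from a precision calculation.
- **Pairing (Methods).** The laboratory machine was used for a full assessment. For the portable machine, "The measurement was then repeated in every patient in only the MCA on each side of the head using the portable Zonare Z-One scanner".
- **Why TAMM (Methods).** "the TAMM velocities were compared because stroke risk categorisation according to the STOP trial was based on TAMM velocity".
- **Categories (Methods).** "Each study was categorised as normal, conditional, abnormal or inadequate according to criteria previously developed by the STOP protocol". The numerical cut-points are not given.
- **Analysis (Statistical Analysis).** Spearman coefficients, an ICC judged against 0.75, and Bland-Altman: "BlandAltman plots were used to estimate the agreement between TAMM velocity measurements by determining how much the velocity from one machine differs from another". No agreement margin is given, the differences are not related to a cut-point, and no statistic for category agreement is named.
- **Conclusion.** "This study demonstrated complete agreement in stroke risk categorisation between the two instruments". The text then asks for more patients over a wider TAMM range, and ends: "Further evidence is needed in order to establish the implications these differences may have on screening".

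**The concern.** The velocity analysis and the category statement never meet. The stated reason for analysing TAMM is that it determines the STOP category, so the useful question about a between-machine difference is how often it moves a child across a cut-point. The plan stops at the size of the difference. Screening impact is then carried by a bare report that categories agreed, in which a pair of readings just beside a cut-point counts the same as a pair far from it.

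At stake is what the study can say about using the portable machine for screening. A favourable ICC, an unremarkable Bland-Altman plot and full category agreement in about 25 children can all occur together with a material chance of switching near a cut-point. Nothing in the planned analysis would show this.

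**Working it through.** The plan gives no calculation behind its 25 patients, so there is no figure to reproduce. It also gives no bias, SD of differences, TAMM distribution or cut-points, so steps 2 to 4 rest on stated assumptions.

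**1. What full agreement supports.** Input: n = 25 (Methods), assuming every child was classifiable on both machines. The exact two-sided 95% upper limit for 0 events is 1 − 0.025^(1/n).
- n = 25: 1 − 0.025^(1/25) = 13.7%.
- n = 20 classifiable: 1 − 0.025^(1/20) = 16.8%.

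**2. What the paired velocities could add.** Let b be the mean difference, s the SD of differences, and d the distance of the laboratory TAMM from a cut-point. If differences are normal with constant b and s, the chance that the portable reading falls across the cut-point is Φ((b − d)/s), with b counted positive towards the cut-point. With b = 0:

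| d (cm/s) | s = 5 | s = 10 | s = 15 | s = 20 |
|---|---|---|---|---|
| 10 | 2% | 16% | 25% | 31% |
| 20 | <0.1% | 2% | 9% | 16% |
| 30 | about 0% | 0.1% | 2% | 7% |

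Bias matters too. With s = 10 and d = 10, a bias of 10 towards the cut-point gives Φ(0) = 50%, and 10 away from it gives Φ(−2) = 2%.

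Precision at n = 25, taking one independent difference per child:
- With b = 0 and s = 10, the simulated 95% interval is about 7% to 31% at d = 10 and 0.4% to 10% at d = 20.
- Each Bland-Altman limit has half-width 2.064 × √(1/25 + 1.96²/48) = 0.715 s.
- The SD itself is known to within a factor of 0.78 to 1.39.

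**3. Can the planned analyses look good while switching is present?** Assume a standardised laboratory TAMM X ~ N(0,1), a portable reading Y = X + N(0, s²), and one cut-point k. Here s is in between-child SDs. The ICC is 1/(1 + s²/2): 0.957 for s = 0.30 and 0.908 for s = 0.45, both well above 0.75.

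| s | k | Discordance p | All 25 match, (1 − p)^25 | Of those above k on X, share below on Y |
|---|---|---|---|---|
| 0.30 | 1.5 | 3.2% | 44% | 18% |
| 0.30 | 2.0 | 1.4% | 70% | 20% |
| 0.45 | 1.5 | 5.0% | 28% | 23% |
| 0.45 | 2.0 | 2.3% | 56% | 26% |

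**4. How far the model can be trusted.** In these scenarios the expected number of children above the cut-point is 25 × (1 − Φ(k)): 1.7 for k = 1.5 and 0.6 for k = 2. The chance that none is above it is Φ(k)^25: 18% and 56%. Spread near the cut-point is then largely borrowed from mid-range children.

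Suppose instead that the spread is proportional to velocity, with assumed mean 110 and SD 25 cm/s and the same root-mean-square spread. For s = 0.30 and k = 1.5:
- The cut-point is 110 + 1.5 × 25 = 147.5, and a child 2s above it reads 147.5 + 2 × 7.5 = 162.5.
- The local SD is 162.5 × 7.5/√(110² + 25²) = 10.8.
- The switch chance is Φ(−15/10.8) = 8%, against Φ(−2) = 2% under constant spread.

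Over the four scenarios this chance is 8% to 11%. True overall discordance becomes 4.0%, 2.0%, 6.0% and 3.1%, so the constant-spread rates in step 3 are 17% to 28% too low.

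**The case against.** The strongest reply is that this is a short degree pilot that already uses Bland-Altman, says it needs more patients over a wider range, and openly leaves the screening question to later work. Much of that stands.

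A reader might infer that the paired data already give the chance of a category switch, whatever the number of children near a cut-point, and that the deferral is therefore unjustified. The documents do not support this. A switch probability follows only from a model for the differences, and step 4 shows how thin the information near a cut-point may be and how much a wrong spread assumption matters. Under the step 3 model, estimating the switch rate from velocities gives a standard error 2.3 to 3.0 times smaller than counting matches. That gain holds only if the model is right. Pairing every mean TAMM with every observed difference avoids normality and cuts the variance about 1.6-fold, but still assumes constant spread.

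A reader might also infer that the portable machine misclassifies children. Nothing supplied shows that, and the scenarios are assumptions.

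Further limits stand:
- Pairing is confined to the MCA, so any estimate concerns MCA-based category only.
- The inadequate category is not a velocity cut.
- No same-machine repeat is described, so the differences mix machine and repeat-scan variation.
- The last sentence may refer to differences at extreme velocities, since the sentence before it does.
- No results section is supplied, so a comparison with the cut-points reported elsewhere cannot be excluded.
- That categories were simply scored as matching or not is inferred from the Conclusion.

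None of this supplies the missing link between the differences and the cut-points, or an interval for the agreement claim.

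**Conclusion.** The point holds in a limited form. The plan compares TAMM because it defines the STOP category, yet never sets the differences against the cut-points, and the agreement statement carries no uncertainty. With 25 classifiable children, full agreement is compatible with discordance up to 13.7%. Under the assumed scenarios, every planned measure can look favourable while roughly a fifth to a quarter of children above a cut-point read below it on the portable machine.

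The collected data allow a provisional estimate that would inform this question but not settle it. Asking for further evidence is reasonable. Leaving out the provisional estimate and the interval is the shortcoming. The 13.7% rests only on the denominator. All switch probabilities rest on assumed bias, spread and TAMM distribution. This is a worthwhile, low-cost improvement to the reporting rather than a defect that invalidates the study.

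**What to change.** After the Bland-Altman sentence in Statistical Analysis, add text to this effect:

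> Report the mean difference and 95% limits of agreement for MCA TAMM, with confidence intervals that allow for two sides per child, and set them against each STOP velocity cut-point. Tabulate the estimated probability that the portable reading falls in a different MCA-based velocity category, by distance of the laboratory TAMM from the cut-point, with portable-lower and portable-higher shown separately and a bootstrap 95% CI resampling children. Check whether the differences vary with velocity; if they do, model the spread or use a log scale. State how many children lie near each cut-point.

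Beside it, show the raw category cross-table, including inadequate studies, with an exact confidence interval for discordance.

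In the Conclusion, qualify the agreement statement with that interval and the provisional switch estimate. State that the differences combine machine and repeat-scan variation. Keep the call for further evidence, and extend it to velocities near the cut-points where few children were observed.

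Cost: a few lines of text, one table and a short bootstrap on data already collected, with no new patients or scans. The downside is that the estimate is model-dependent and imprecise at n = 25, and the conclusion may read less favourably.
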